6.2 Expedited Event Reporting

The Investigator is required to report to the Sponsor any UADEs/USADEs within 24 hours and all SAEs within 72 hours after first learning of the event (see Table 2). All expedited events will be reported to the Sponsor primarily via site entry of the event into the eCRFs. If unable to access database to meet reporting timelines, then the expedited event information can be provided via fax at [[name]]([contact]). Site reported entry of the event into the eCRFs should promptly follow. Subsequent to reporting the event via site entry of the eCRFs or fax, the Investigator will fax and/or email all available supporting documentation (de-identified as to the Subjects' identity) to the Sponsor.

As additional information becomes available, copies of that source documentation which contain significant information related to the event such as progress notes, consultations, nurse's notes, operative reports, imaging studies and Subject summaries etc. are requested for a complete evaluation of the event.

Table 2. Expedited Adverse Event Reporting Requirements

UADEs/USADEs	Investigator will notify Sponsor of all UADEs and USADEs within 24 hours of being aware of the event.
SAEs	Investigator will notify Sponsor of all SAEs within 72 hours of being aware of the event.
Sponsor contact information:	[contact] Email: [contact]

In regard to Subject deaths, it is requested that a copy of the death certificate and a copy of the autopsy report, if applicable, be sent to the Sponsor when available. Any other source documents related to the death should also be provided to the Sponsor. In the event that no source documents are available, the Principle Investigator (PI) is requested to describe the circumstances of the Subject's death in a letter, e-mail or other written communication.

UADEs/USADEs have expedited reporting requirements. Any event that meets the definition of UADE (Section 6.1) must be reported to FDA, all Investigators and reviewing IRBs within 10 working days after becoming aware of information that an UADE has occurred. The investigator must also follow their local IRB requirements for SAE/UADE/USADE reporting.

The site will notify the reviewing IRB within 10 working days after becoming aware of the effect. The Sponsor will notify the all Investigators, IRBs and the FDA within 10 working days after first receiving notification of the event. In addition, the Sponsor will comply with Medical Device Reporting / MDR regulations where applicable.

6.3 Adverse Event Reporting

All adverse events (not meeting expedited reporting criteria) will be reported by site entry of the eCRFs in a timely manner.

7 DEVICE-SPECIFIC EVENT

A device-specific event is any malfunction or deficiency of the device.

Device deficiency is defined as inadequacy of a medical device with respect to its identity, quality, durability, reliability, safety or performance (ISO 14155:2011 3.15)

Malfunction is defined as a failure of an investigational device to perform in accordance with the Instructions For Use or Clinical Investigational Plan (ISO 14155:2011 3.27)

All device-specific events, malfunctions or deficiencies must be reported to both the Sponsor and local authorities as required by governing law. If a device malfunction results in an adverse event, this adverse event will be considered reportable to the Sponsor.

8 STUDY COMMITTEE / CORE LABORATORY

To avoid and minimize bias, an independent Clinical Events Committee (CEC) and Imaging Core Laboratory will be in place to assess AE relationship and device migration, respectively.

8.1 Clinical Events Committee

A CEC will be in place for the study using a minimum of three (3) physicians knowledgeable in the treatment and embolization of brain AVMs. This committee will be responsible for the review and adjudication of all study AEs.

The CEC will adjudicate to specified event definitions (where available), event relatedness, event severity, and event outcome.

The CEC can request additional source documentation and any potential imaging obtained in support of the AE to assist with adjudication. The CEC is expected to meet, at a minimum, each quarter.

8.2 Imaging Core Laboratory

For Subjects in whom the catheter or catheter tip is retained, 30-day, and 12-month imaging will be obtained to assess potential catheter tip migration. Thirty-day imaging will also be collected if it is performed as a result of physician discretion.

Any subsequent imaging obtained as standard of care during participation in the study will be documented on the eCRFs and may be collected.

9 STATISTICAL METHODS

9.1 Sample Size and Safety Performance Goal

The maximum number of Subjects to be enrolled into this clinical investigation is 161 (with 13% attrition included). To establish safety performance goal for the primary endpoint, literature research was conducted on the reported data of catheter retention. Table 3 summarizes the rates from the peer-reviewed literature. The rate ranges from 1% to 9.7% with an un-weighted average rate of 5.8% and weighted average of 5.7%. The one-sided 95% upper confidence interval for the individual studies ranged from 4.6% to 16.3%.

Table 3. Event Rate Based on Literature Review

Citation	Purpose	Catheter*	Country	Catheter Retainment Frequency (pts)	One-Sided 95% Upper Bound **
Gao, K et al. Chinese Med J 2009; 122:1851-1856.	Onyx delivery	M, U	China	5/115 = 4.4%	8.9%
Katsaridis, V et al 2008 Neuroradiology 2008; 50: 589-597.	Onyx delivery bAVM	M, U	Greece	1/101 = 1%	4.6%
Mounayer, C et al AJNR 2007; 28: 518-523.	NBCA, Onyx delivery bAVM	F, U	France	4/94 = 4.3%	9.5%
Panagiotopoulos, V et al AJNR 2009; 30: 99-106.	Onyx delivery bAVM	M, U	Germany	1/82 = 1.2%	5.7%
Saatci, I et al J Neurosurg 2011; DOI: 10 3171/2011.2 JNS 09830.	Onyx, NBCA delivery bAVM	F, U, M	Turkey	28/350 = 8.0%	10.8%
Song, D et al. Intervent Neuroradiol 2005; 11 (SUPPL. 1): 179-184.	Onyx delivery BAVM	M, U	China	3/50 = 6.0%	14.8%
Weber et al. AJNR 2007; 28: 371-377.	Onyx Delivery bAVM	U	Germany	9/93 = 9.7%	16.3%
Un-weighted Average					51/885 = 5.8%
Weighted Average					5.7%

*M = Marathon; U = UltraFlow; E = Echelon; F = FlowRider.

**95% one-sided upper bound is calculated using the Exact method.

The weighted average of catheter retention event from the table above was used as an estimate of the primary endpoint event rate for this study. Based on a sample size of 161 (maximum sample size), if

the event rate is 5.6%, the 95% upper bound is 9.6%. The 5.6% event rate is a conservative estimate calculated by using the weighted average of 5.7% rounded down to account for a whole patient.

Based on the one-sided 95% upper-bound it is proposed that the performance goal for the primary endpoint be 9.6%. The one-sided 95% upper confidence bound of the observed primary endpoint event rate will be compared to 9.6%. If this upper bound is less than 9.6%, then it is considered that the Apollo™ micro catheter device meets the primary endpoint performance goal.

9.2 Data Analysis Plan

9.2.1 General Principles

All statistical analyses will be performed using Statistical Analysis System (SAS) for Windows (version 9.2 or higher, SAS Institute Inc. Cary, NC) or other widely accepted statistical or graphical software. In general, data for all study Subjects combined will be presented. Individual data will be presented in Subject listings.

Descriptive statistics will be used to present the data and to summarize the results. Discrete variables will be presented using frequency distributions and cross tabulations. Continuous variables will be summarized by presenting the number of observations (N), mean, standard deviation, median, minimum, and maximum values.

For adverse event reporting, which includes the primary and secondary endpoints, the primary analysis will be based on Subject counts (e.g., the number and percentage of Subjects with event among the total number of Subjects). The data will be presented in the format of $p\% (x/N) [e]$, with p and x being the percentage and number of Subjects with events, respectively, N being the sample size of the analysis population, and e being the total number of events occurred in the x Subjects. For example, the data of 3.1% (5/161) [8] indicates that a total of 8 events occurred in 5 Subjects out of a total of 161 Subjects (3.1%). In addition, the data based on device (e.g., the number and percentage of devices with events among the total number of deployed devices) will also be provided.

9.2.2 Analysis Samples

Results will be presented based on two populations:

- Intention to Treat (ITT), defined as all Subjects consented and enrolled, independent of the study device being deployed
- Full Analysis Set (FAS), defined as all Subjects consented and enrolled where the study device was deployed, independent of the success of the procedure

All reported adverse events will be presented based on the ITT population and the success of the study will be based on the FAS.

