3.2 Acute Secondary Endpoints (30 days)

- Rate of premature (unintentional) catheter tip detachment
 - Unintentional tip detachment is defined as detachment of the catheter tip within the vasculature at an unintended location.
- Rate of intentional catheter tip detachment
 - Intentional catheter tip detachment is defined as deliberately applying the necessary force on the catheter to detach catheter tip.
- Rate of migration of the retained catheter tip post embolization
- Incidence of procedure-related AEs
- Rate of catheter/tip leakage from detachment zone

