5.5 Screen Failure

Subject will be considered a screen failure if:

- The Subject signs the ICF but fails to meet study inclusion/exclusion criteria during the screening and baseline phase.
- The Subject signs the ICF, meets the study inclusion/exclusion criteria but an attempt to use the Apollo™ micro catheter is not performed.

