5.6 Enrollment

A Subject will be considered enrolled once the Apollo™ micro catheter is advanced inside the blood stream of the Subject.

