9.2.9 Handling of Missing Data

For the primary endpoint, the assessment is done peri-procedurally and it is projected that there will be minimal reduction in the eligible population based on the time of the measurement. Therefore, no imputations are planned for the primary endpoint. The above-mentioned potential sample size attrition is likely due to enrolled Subjects not treated with study device or subject withdrawals and not due to missing data on primary endpoint.

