
Informed Consent: A process by which a Subject voluntarily confirms his or her willingness to participate in a particular trial, after having been informed of all aspects of the trial that are relevant to the Subject's decision to participate. Informed consent is documented by means of a written, signed and dated informed consent form.

Intent-to-Treat: All Subjects consented and enrolled, independent of the study device being deployed.

Investigator: An individual who actually conducts a clinical investigation, i.e., under whose immediate direction the test article is administered or dispensed to, or used involving, a Subject, or, in the event of an investigation conducted by a team of individuals, is the responsible leader of that team.

Monitoring: An individual who oversees the progress of an investigation.

Screen Failure: Subjects who sign the ICF and subsequently fail to meet all of the inclusion/exclusion criteria, and do not receive the study device will be considered screen failures. Upon determination that the patient does not qualify for this study, the reason for termination will be documented and Subjects will not be followed per the investigational plan requirements.

Serious Adverse Event (SAE): Adverse Event that
 
A. Led to death,B. Led to serious deterioration in the health of the Subject, that either resulted in
a. A life-threatening illness or injury, orb. A permanent impairment of a body structure or a body function, orc. In-patient or prolonged hospitalization, ord. Medical or surgical intervention to prevent permanent life-threatening illness or injury or permanent impairment to a body structure or a body function,C. Led to fetal distress, fetal death or a congenital abnormality or birth defect (ISO 14155:2011) 
Note 1: This includes device deficiencies that might have led to a serious adverse event if a) suitable action had not been taken or b) intervention had not been made or c) if circumstances had been less fortunate. These are handled under the SAE reporting system.
 
Note 2: A planned hospitalization for pre-existing condition, or a procedure required by the Clinical Investigational Plan, without a serious deterioration in health, is not considered to be a serious adverse event.

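### Success is judged in the FAS, and 'deployed' is undefined; if it means more than entry into the blood stream, an endpoint event that prevents deployment drops out of the 9.6% test.

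*Combined protocol and SAP*

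**What the plan says.** Section 9.2.2 names two populations and assigns them different jobs: "All reported adverse events will be presented based on the ITT population and the success of the study will be based on the FAS". The FAS is "defined as all Subjects consented and enrolled where the study device was deployed, independent of the success of the procedure". The ITT set in the glossary (Appendix A) is "All Subjects consented and enrolled, independent of the study device being deployed", and Section 9.2.2 defines it the same way. Neither Section 9 nor the glossary says what deployment is.

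Two earlier sections fix who can be in either set. Under Section 5.6 a subject is enrolled once the Apollo "micro catheter is advanced inside the blood stream of the Subject". Under Section 5.5 a consented subject who "meets the study inclusion/exclusion criteria but an attempt to use the" catheter is not made is a screen failure. Every enrolled subject has therefore been exposed to the device inside the vasculature.

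Section 9.2.4 compares the exact one-sided upper bound for the subject-level event rate with 9.6%. The bound is at 96% when 80 subjects have reached 30 days and at 95% at the end. Two of the three endpoint components are premature tip detachment and catheter rupture, break or fracture, each with clinical sequelae. Section 3.2 defines the first by place only: "Unintentional tip detachment is defined as detachment of the catheter tip within the vasculature at an unintended location".

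**The concern.** The endpoint can be met as soon as the catheter is in the vasculature, but membership of the decision set depends on a further, undefined step. If that step comes after navigation, a catheter that detaches or fractures on the way and causes a deficit may also be the reason why nothing was deployed. The safety event then removes its own subject from the safety test. Section 9.2.2 keeps a subject whose procedure was unsuccessful, but only once deployment has taken place. Listing the event in the ITT tables keeps it visible without changing the success decision.

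Few events are allowed, at most 9 of 161 at the final look and 2 of 80 at the interim, so one or two subjects can settle the outcome.

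**Working it through.** **1. What deployment can mean.** Set side by side, the passages do not settle it.

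- *Something later than entry.* The ITT wording, which disregards deployment, would be empty if every enrolled subject counted as deployed. Section 9.2.9 says the "attrition is likely due to enrolled Subjects not treated with study device or subject withdrawals", so it expects enrolled subjects who are not treated.
- *General use.* Section 9.2.1 counts "the number and percentage of devices with events among the total number of deployed devices", which would leave out events in undeployed devices unless the term is wide. Section 9.2.6 treats procedure and deployment as interchangeable.

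If deployment means entry into the blood stream, FAS and ITT are the same set and there is no gap. The steps below apply to the later meaning.

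**2. The plan's own figures.** The exact one-sided upper bound is U(x, n; c) = the c-quantile of Beta(x + 1, n − x). Section 9.1 uses a 5.6% rate at n = 161, which is 9/161. U(9, 161; 0.95) = 9.55%, which rounds to the stated 9.6%. The attrition figure also reproduces: 140 / (1 − 0.13) = 160.9, so 161. The allowance is 161 − 140 = 21 subjects. That is a ceiling for exclusions, because Section 9.2.9 also attributes attrition to withdrawals.

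**3. Largest passing counts against 9.6%.**

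| Look | n | Most events that pass |
|---|---|---|
| Final, 95% | 134–147 | 7 |
| Final, 95% | 148–160 | 8 |
| Final, 95% | 161 | 9 |
| Interim, 96% | 67–81 | 2 |
| Interim, 96% | 82–96 | 3 |

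**4. Final look, 161 enrolled.**

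- All enrolled: 10/161 gives 10.31%, fail.
- One subject excluded, with an event: 9/160 gives 9.61%, still a fail.
- Two subjects excluded, both with events: 8/159 gives 8.90%, pass.
- Two excluded events are enough with 2 to 13 subjects excluded in total (8/148 gives 9.54%).
- With 14 to 21 excluded, three are needed (7/140 gives 9.19%, while 8/140 gives 10.07%).

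**5. Interim look.**

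- If the 80 are enrolled subjects: 3/80 gives 9.79%, fail. With one event excluded, 2/79 gives 8.11%, pass, and early success is claimed.
- If the 80 are FAS subjects, the same reversal needs exactly one excluded subject: 3/81 gives 9.67% (fail) against 2/80 at 8.01% (pass). With two excluded, 3/82 already passes at 9.56%.
- At a true rate of 9.6%, the same in both groups and with 80 enrolled, the chance that the FAS passes while all 80 fail is 0.1%, 0.7% and 1.6% with 1, 5 and 10 excluded.

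**6. The opposite direction.** Excluding event-free subjects makes the test stricter: 9/161 passes (9.55%), 9/160 fails (9.61%). At the final look with 21 excluded and a 5.6% rate in both groups, let X ~ Bin(140, 0.056) be events in the FAS and Y ~ Bin(21, 0.056) events among the excluded. The FAS is stricter when X ≥ 8 and X + Y ≤ 9, which has probability 13.3%. It is more lenient when X ≤ 7 and X + Y ≥ 10, which has probability 2.0%. With one excluded the figures are 12.8% and 0%.

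**7. The rule under Fix.** Adding enrolled subjects with an event back to the FAS gives (8 + 2)/(159 + 2) = 10/161, fail, and at the interim (2 + 1)/(79 + 1) = 3/80, fail. With no such event the FAS result is unchanged.

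**The case against.** The strongest reply is that this is a loose word and not a faulty rule. Sections 9.2.1 and 9.2.6 use deployment for general use of the device, and on that reading nothing is lost. Even on the later reading the path is narrow: the event must come before deployment, must carry clinical sequelae, and must occur in a subject with no deployment at any stage. About two catheters per subject are expected and staged procedures are allowed. Any later deployment brings the subject, and the event, back into the FAS. The third component, a retained catheter body, will normally follow embolic delivery, since Section 1.2.2 attributes entrapment to the cast or to vasospasm from the embolic. All of this stands and limits the size of the point. It does not remove it, because Sections 9.2.2 and 9.2.9 point toward the later meaning. Section 1.3.1 reports failed access (n=9) and delivery catheter rupture (n=2) in the earlier randomized trial of Onyx. Those were not Apollo catheters and give no rate for this study, but they show that such failures happen.

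Three stronger readings are tempting and are not supported:

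- *That the FAS favours the device.* At equal risk the FAS is more often the stricter set (step 6). At a true 9.6% in both groups, the chance of success over both looks is 5.5% in either set (70 of 80 in the FAS at the interim, 140 of 161 at the end, no sample size change).
- *That no rule covers disagreement between the sets.* Section 9.2.2 says the FAS decides.
- *That success should move to the TT-type set of all enrolled subjects alone, or require both bounds to pass.* If the treated rate is 9.6% and excluded subjects are event-free, testing all enrolled subjects alone succeeds 13.6% of the time, against 5.5% for the FAS. Requiring both bounds is a debatable preference, and it lowers success at equal risk from 51.0% to 47.7% at the 5.6% rate. The gap can be closed without either.

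**Conclusion.** The point holds in a conditional form. Deployment is undefined, and part of the plan's wording implies a step beyond enrollment. On that reading an endpoint event can take its own subject out of the success decision. The documents give no expected number of such subjects, and it may be zero. What is shown is fragility: two excluded events at 161 enrolled (with 2 to 13 excluded in total), or one at an interim of 80 enrolled, can turn a fail into a pass. This rests on the later meaning of deployment, on no deployment at any stage in those subjects and, for the interim figure, on the 80 being enrolled subjects. It deserves correction because the analysis set of a safety test should not depend on the safety outcome, and because the correction is small.

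**What to change.** In Sections 9.2.2 and 9.2.4:

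1. State that a primary endpoint event in any subject in whom the Apollo catheter entered the blood stream counts in the comparison with 9.6%, at both the interim and the final look. The FAS stays the decision set, with any enrolled subject who has such an event added to numerator and denominator.
2. Report the exact bound in all enrolled subjects alongside, as supportive.
3. Define deployment. If it is set equal to the enrollment point in Section 5.6, FAS and ITT coincide and item 1 is met automatically.
4. State whether the 80 interim subjects are enrolled or FAS subjects.

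The cost is a few sentences and no new data. Item 1 adds event subjects but not undeployed event-free ones, so the test becomes slightly stricter if such an event occurs. If none occurs, the result is the same as under the present rule.

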9.2.3 Analysis Baseline Demographics and Procedural Characteristics

Descriptive statistics will be generated for pre-intervention demographics, procedural characteristics, and follow-up data collected. Categorical variables will be analyzed using

frequency, incidence, and event rate. For continuous variables collected in the study, analysis will include mean, median, standard deviation, and range.

9.2.4 Analysis of Primary Endpoint

The primary endpoint is the composite of any of the following catheter related adverse events:

- Premature (unintentional) catheter tip detachment with clinical sequelae
- Catheter rupture/break/fracture with clinical sequelae
- Retained catheter body in the vasculature

The primary analysis for the primary endpoint is based on Subject counts, not event counts. A Subject with more than one event will be counted only once toward the event rate based on the total number of Subjects with adverse events. An event rate based on event counts will also be presented. For example, if a Subject experiences one "Premature (unintentional) catheter tip detachment with clinical sequelae" and one "Retained catheter body in the vasculature", the Subject will be counted once in the rate of total Subjects with primary endpoint; the same Subject will be counted once in the individual event category of "Premature (unintentional) catheter tip detachment with clinical sequelae" and once in the "Retained catheter body in the vasculature" category.

The primary endpoint will be summarized as the event rate per Subject with a one-sided 95% upper confidence bound using the Exact method. The upper bound will be compared to the performance goal of 9.6%. If this upper bound is less than 9.6%, it is considered that the Apollo™ micro catheter meets the primary objective.

One interim analysis is planned for this study. An interim assessment will be performed when 80 subjects have reached the 30-day follow-up. If the one-sided 96% upper confidence bound is below the pre-specified threshold of 9.6%, the primary safety objective is considered to be met and early trial stop for success will be claimed. On those subjects already enrolled, follow-up will continue according to the protocol. Otherwise, the trial will continue and the final analysis will be performed at the end of study. The 96% confidence level is used for the interim analysis to ensure the overall type I error is controlled at the 0.05 level. In addition, the conditional power will be calculated at the interim analysis to determine if a sample size adjustment is necessary. It will not be necessary to adjust the alpha level if the conditional power is greater than 50% (Chen et al., 2004). However, in case that the conditional power is below 50%, the procedure of Cui et al. (1999) will be followed to ensure the study-wise type I error rate is well controlled.

The event rates based on device counts will also be provided.

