
PROTOCOL SYNOPSIS	
Sponsor: Micro Therapeutics, Inc. d/b/a ev3 Neurovascular [name]	Protocol Number: NV-APL001 Revision: A, 05-Aug-2014 Product: Apollo™ Onyx™ Delivery Micro Catheter Regulatory Class: Class III Development Phase: Phase IV
Background (cont.): Given the potential side effects of catheter retention and increased procedural risk associated with alternative methods necessary for removing entrapped catheters, a catheter technology that will not leave behind the entire length of a micro catheter is needed. This led to the development of the Apollo™ Onyx™ Delivery Micro Catheter. In the event of catheter retention, using the Apollo™ Onyx™ Delivery Micro Catheter versus any other standard micro catheter represents leaving behind a 1.5-3.0 cm long detachable tip in the Onyx™ cast versus an average 165 cm long catheter in the vasculature.	
Number of Subjects: 161 Subjects with estimated 322 catheter utilizations (~ 2 catheters per Subject)	Number of Study Centers: Up to 25 sites across the United States
Duration of Study: 
• Enrollment: 30 months• Follow-up period: Up to 12 months• Total Study Duration: Up to 42 months	
Primary Composite Endpoint (30 days): Incidence of catheter-related adverse events per Subject: 
• Premature (unintentional) catheter tip detachment with clinical sequelae*• Catheter rupture/break/fracture with clinical sequelae*, and• Retained catheter body in the vasculature	
*Clinical sequelae are defined as all focal neurologic deficits related to lesions within the vascular territory catheterized.	
Acute Secondary Endpoints (30 days): 
1. Rate of premature (unintentional) catheter tip detachment2. Rate of intentional catheter tip detachment3. Rate of migration of the retained catheter tip post embolization4. Incidence of procedure-related adverse events5. Rate of catheter/tip leakage from detachment zone	
Long-Term Secondary Endpoints (12 months): 
1. Incidence of adverse events (AEs)2. Rate of migration of the retained catheter tip post embolization	

[figure not shown]
PROTOCOL SYNOPSIS	
Sponsor: Micro Therapeutics, Inc. d/b/a ev3 Neurovascular [name]	Protocol Number: NV-APL001 Revision: A, 05-Aug-2014 Product: Apollo™ Onyx™ Delivery Micro Catheter Regulatory Class: Class III Development Phase: Phase IV
Clinical Events Committee (CEC):	

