Statistical Analysis: The primary endpoint will be summarized as the event rate per Subject with a one-sided 95% upper confidence bound using the Exact method. The upper bound will be compared to the performance goal of 9.6%. If this upper bound is less than 9.6%, it is considered that the Apollo™ micro catheter meets the primary objective. Additionally, an interim analysis will be performed when 80 subjects have reached the 30-day follow-up. The interim prediction power will be calculated and the sample size may be adjusted as appropriate. Adverse events for all enrolled Subjects will be collected and reported. For adverse event reporting, which includes the primary and secondary endpoints, the primary analysis will be based on Subject counts (e.g., the number and percentage of Subjects with event among the total number of Subjects). The data will be presented in the format of $p\%$ (x/N) [e], with p and x being the percentage and number of Subjects with events, respectively, N being the sample size of the analysis population, and e being the total number of events occurred in the x Subjects. For example, the data of 3.1% (5/161) [8] indicates that a total of 8 events occurred in 5 Subjects out of a total of 161 Subjects (3.1%). In addition, the data based on device (e.g., the number and percentage of devices with events among the total number of deployed devices) will also be provided.	

PROTOCOL SYNOPSIS

Sponsor: Micro Therapeutics, Inc. d/b/a ev3 Neurovascular [name]	Protocol Number: NV-APL001 Revision: A, 05-Aug-2014 Product: Apollo™ Onyx™ Delivery Micro Catheter Regulatory Class: Class III Development Phase: Phase IV
---------------------------------------------------------------------------------------------------------------	-----------------------------------------------------------------------------------------------------------------------------------------------------------------------------------------------------------

Sample Size Justification:

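### The 96% interim level does not secure an overall type I error of 0.05, because the final test still uses the full one-sided 95% exact bound and the interim analysis set is not defined

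*Combined protocol and SAP*

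**What the plan says.** The primary test is in section 9.2.4: "The primary endpoint will be summarized as the event rate per Subject with a one-sided 95% upper confidence bound using the Exact method". Success requires that bound to fall below 9.6%. The Synopsis (Statistical Analysis) gives the same final criterion, a "one-sided 95% upper confidence bound using the Exact method".

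Section 9.2.4 adds one interim look: "An interim assessment will be performed when 80 subjects have reached the 30-day follow-up". If the one-sided 96% bound is then below 9.6%, the objective is met and the trial stops for success. If not, it runs on to the final analysis. On error control the section says: "The 96% confidence level is used for the interim analysis to ensure the overall type I error is controlled at the 0.05 level".

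The section also cites two published procedures for protecting the error rate, chosen according to whether conditional power is above or below 50%. Both are tied to changing the sample size.

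Section 9.2.2 says "the success of the study will be based on the FAS". Section 9.1 says "The maximum number of Subjects to be enrolled into this clinical investigation is 161 (with 13% attrition included".

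**The concern.** There are two chances to declare success, at nominal levels of 4% and then 5%. If the second test already spends close to 5%, any success at the first look that would not have recurred at the end is additional error. A stricter interim level limits that addition but cannot remove it while the final level is unreduced. The plan gives no spending function, no adjusted final level and no calculation to support its statement.

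The second gap is the interim data set. The 80-subject figure says when the look happens, not whose data are analysed. It could mean exactly 80 subjects, everyone with 30-day data at the cut, or only those of the 80 who are in the FAS. With an exact test, the success cut-off can move by a whole event when one or two subjects are added.

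This is the study's only confirmatory test, so the error-control statement supports the main conclusion.

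**Working it through.** **Inputs.** Goal and null rate p = 9.6%, interim level 96%, final level 95%, interim trigger 80 (section 9.2.4). Maximum size 161 and 13% attrition, so 161 × 0.87 = 140.07, about 140 analysed (section 9.1). Assumed event rate 5.6% (section 9.1). No sample size change is assumed.

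**Reproducing the plan's figure.** 5.6% of 161 is 9 events. The exact 95% upper bound for 9/161 is 9.55%, which rounds to the stated 9.6%.

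**Cut-offs.** The exact upper bound for x events in n is the Beta(x+1, n−x) quantile at the chosen level. The cut-off is the largest x whose bound is below 9.6%.

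- Interim, 80 subjects, 96%: 2/80 gives 8.0% and 3/80 gives 9.8%, so success needs 2 or fewer.
- Final, 161 subjects, 95%: 9/161 gives 9.55%, so success needs 9 or fewer.
- Final, 140 subjects, 95%: 7/140 gives 9.19%, so success needs 7 or fewer.

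**Overall error.** With n1 subjects at the interim and cut-off c1, and N subjects at the end with cut-off c:

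error = P(X1 ≤ c1) + Σ over x > c1 of P(X1 = x) × P(X2 ≤ c − x), where X1 ~ Bin(n1, 0.096) and X2 ~ Bin(N − n1, 0.096).

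- N = 161: 0.0141 + 0.0408 = 0.0549. The final look alone has error 0.0480, so almost no room was left for a second look.
- N = 140: 0.0426. The final look alone has error 0.0358, and the unused 1.4 points absorb the interim.

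With exactly 80 at the interim, the error exceeds 0.05 at 3 of the 22 final sizes from 140 to 161: 5.40% at 148, 5.18% at 149 and 5.49% at 161. At 160 it is 3.41%. That drop of about two points between 160 and 161 shows that the control comes from discreteness, not from the choice of 96%. A normal approximation, which removes discreteness, gives 7.28% at 161 and 7.06% at 140.

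**Varying the interim set.**

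| Subjects at interim | Interim cut-off | Error at N = 161 | Error at N = 140 | Final sizes 140–161 above 0.05 |
|---|---|---|---|---|
| 70 | 2 | 6.69% | 5.51% | 16 of 22 |
| 75 | 2 | 5.95% | 4.75% | 6 of 22 |
| 80 | 2 | 5.49% | 4.26% | 3 of 22 |
| 81 | 2 | 5.42% | 4.19% | 3 of 22 |
| 82 | 3 | 7.09% | 5.92% | 22 of 22 |
| 85 | 3 | 6.54% | 5.34% | 14 of 22 |
| 90 | 3 | 5.87% | 4.63% | 5 of 22 |

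The jump at 82 occurs because 3/82 has a 96% bound of 9.56%, just under the goal, whereas 3/81 gives 9.67%. The first look alone then has error 3.90%. The Synopsis gives "Enrollment: 30 months". Assuming even accrual, that is 161/30 = 5.4 subjects per month, so two more subjects correspond to a data cut about 11 days later. The 70-subject row assumes that 13% of the 80 fall outside the FAS; the 75-subject row shows a milder loss.

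**Check.** Simulation with 4 million runs gave about 5.5% (80, then 161), 4.26% (80, then 140) and 7.10% (82, then 161).

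**The case against.** The strongest reply is that the claim holds where the plan expects to be. The 161 includes attrition, so about 140 subjects should be analysed; with exactly 80 at the interim, the error there is 4.26%, and 19 of the 22 sizes from 140 to 161 meet 0.05. The 5.49% needs no attrition, is only 0.49 point over, and depends on the goal having been rounded up: with the unrounded 9.552% as goal and null, 9/161 would no longer pass and the error would be 3.42%.

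All of that is correct, but it does not rescue the statement. The operative criterion is the rounded one: "The upper bound will be compared to the performance goal of 9.6" per cent. The plan also derives that goal from 161 subjects. At 161 the error is above 0.05 at every interim size in the table.

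Two further points stand as qualifications. First, 82 is the worst interim size nearby, and the error falls again as more subjects enter, so a later cut does not raise it steadily. Second, the 70-subject case may overstate the loss: enrolment requires the catheter to be in the bloodstream (section 5.6), and subjects who have reached 30 days have mostly passed the point of early withdrawal.

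The cited sample size procedures do not answer the point. They concern a change in size, and the figures here arise with no change. If the size were changed, these figures would no longer apply and the error would need recomputing.

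**Conclusion.** The concern holds. Using 96% at the interim with an unreduced 95% final bound does not guarantee 0.05. With exactly 80 interim subjects the overall error is 5.49% at 161 and 4.26% at 140. If the interim set is allowed to differ, it reaches 7.09% and 5.92% in the least favourable nearby case. Whether 0.05 is met depends on how many subjects enter the interim analysis and how many are in the final FAS; the plan specifies neither number tightly enough. The figures assume a true rate of 9.6%, independent subjects, the stated rounded goal and no sample size change. The excess at exactly 80 is small. The fault is that a stated property of the only confirmatory test is not delivered by the design. It should be fixed.

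**What to change.** 1. State in section 9.2.4 that the interim analysis uses exactly the first 80 evaluable FAS subjects, regardless of how many others have data at the cut.
2. Replace the sentence on error control with paired event-count boundaries, computed exactly so that the overall error is at most 0.05 for the FAS size actually analysed, and recomputed after any sample size change.

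Two pairs that work with exactly 80 at the interim:

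- **(a) 1 or fewer of 80, then 9 or fewer of 161.** Error 4.91%. Keeping the 95% exact final cut-off, the error does not exceed 4.91% at any size from 140 to 161. It can at larger sizes (5.15% at 286), so the recheck is needed.
- **(b) A 96% bound at both looks: 2 or fewer of 80, then 8 or fewer of 161.** Error 3.29%, with a maximum of 4.98% over an assumed range of 120 to 322. This pair relies on step 1: with a 96% bound applied to 82 interim subjects it fails (5.24% at 161, 5.92% at 140).

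**Cost.** Pair (a) lowers the success probability at a 5.6% event rate from 59.6% to 58.7% at 161, and from 48.8% to 47.5% at 140. The chance of an interim claim falls from 17% to 6% at a 5.6% rate, from 57% to 30% at 3%, and from 78% to 52% at 2%. Pair (b) leaves the chance of an interim claim unchanged but lowers the success probability at 5.6% to 47.3% at 161. Pair (a) suits a study whose main interest is the final result; pair (b) keeps the early stop. Either is a change of text only, but section 9.2.4 is part of the protocol, so the amendment and IRB steps in section 13.1 apply.
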